#### 11.6.5. Pharmacodynamic (and / or Biomarker)

Not applicable.

## 11.7. Appendix 7: Reporting Standards for Missing Data

### 11.7.1. Premature Withdrawals

Element	Reporting Detail
General	
 
• Subject study completion was defined as complete all phases of the study including the follow-up visit.
 
• Withdrawn subjects may be replaced in the study, if applicable, at the discretion of the sponsor in consultation with the investigator.
 
• All available data from subjects who were withdrawn from the study will be listed and all available planned data will be included in summary tables and figures, unless otherwise specified.
 
• All subjects who withdraw prematurely from the study/study drug will be documented and the reason for their withdrawal recorded in the final Clinical Pharmacology Study Report (CPSR).
 
• In the event that the study is prematurely discontinued, all available data will be listed and a review carried out by the study team to assess which statistical analyses are still considered appropriate.
 

### 11.7.2. Handling of Missing Data

Element	Reporting Detail
General	
 
• Missing data occurs when any requested data is not provided, leading to blank fields on the collection instrument: 
 
○ These data will be indicated by the use of a “blank” in subject listing displays. Unless all data for a specific visit are missing in which case the data is excluded from the table.
 
○ Answers such as “Not applicable” and “Not evaluable” are not considered to be missing data and should be displayed as such.
 
 
 

Outliers	
 
• Any participants excluded from the summaries and/or statistical analyses will be documented along with the reason for exclusion in the clinical study report.
 

#### 11.7.2.1. Handling of Missing and Partial Dates

Element	Reporting Detail
General	
 
• Partial dates will be displayed as captured in subject listing displays.
 

Adverse Events	
 
• The eCRF allows for the possibility of partial dates (i.e., only month and year) to be recorded for AE start and end dates; that is, the day of the month may be missing. In such a case, the following conventions will be applied for calculating the time to onset and the duration of the event: 
 
○ Missing Start Day: First of the month will be used unless this is before the start date of study treatment; in this case the study treatment start date will be used and hence the event is considered On-treatment as per Appendix 4: Study Phases and Treatment Emergent Adverse Events.
 
○ Missing Stop Day: Last day of the month will be used, unless this is after the stop date of study treatment; in this case the study treatment stop date will be used.
 
 
 
• Completely missing start or end dates will remain missing, with no imputation applied.
 

Element	Reporting Detail
	Consequently, time to onset and duration of such events will be missing.
Concomitant Medications	

● Partial dates for any concomitant medications recorded in the CRF will be imputed using the following convention:

○ If the partial date is a start date, a '01' will be used for the day and 'Jan' will be used for the month

○ If the partial date is a stop date, a '28/29/30/31' will be used for the day (dependent on the month and year) and 'Dec' will be used for the month.

● The recorded partial date will be displayed in listings.

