Sequence 3	Dose 1	Dose 3	Placebo	Dose 7
Sequence 4	Dose 1	Dose 3	Dose 5	Placebo

Cohort 2	Period 1	Period 2	Period 3	Period 4
Sequence 1	Placebo	Dose 4	Dose 6	Dose 8
Sequence 2	Dose 2	Placebo	Dose 6	Dose 8
Sequence 3	Dose 2	Dose 4	Placebo	Dose 8
Sequence 4	Dose 2	Dose 4	Dose 6	Placebo

Part 1 SAD: Sentinel Dosing

To conservatively assess safety, at the start of each dose period of the SAD, 2 out of the 8 participants will serve as sentinel participants with one receiving GSK3640254 and the other receiving placebo. These sentinel participants will be followed clinically for 24 hours after dose administration to monitor for emergence of adverse events. If there are no safety concerns, in the judgment of the PI, on review of the 24-hour safety data (e.g. vital signs, ECGs, and adverse events) for the sentinel participants, the remaining 6 participants will subsequently be administered either GSK3640254 or PBO according to randomization schedules.

Part 1 SAD: Dose Escalation

Dose escalation in Part 1 will be determined by the VH/GSK study team and the PI based on the double-blind (sponsor-unblinded) safety data and the PK data from the current and

previous dose(s). Dose escalation will not exceed approximately 3-fold between doses up to approximately the predicted minimally effective dose and will not exceed 2-fold thereafter. Dose escalation in Part 1 will require (from the current dosing group) at least 24 hours of safety and PK data from 4 participants receiving active drug. Dose escalation will be guided by safety as well as the SAD PK stopping criteria (see Section 8). Due to the alternating dosing periods between Cohort 1 and Cohort 2, a participant in either cohort will receive the next dose after approximately 3 or 4 weeks.

Part 2 (MAD):

Part 2 consists of four ascending repeat-dose cohorts (Cohorts 3 to 6), each with 8 participants (active/PBO=6/2) who will receive a once-daily dose of GSK3640254 or PBO for 14 days. Details of the starting dose and dose escalations in Part 2 (MAD) are provided in Section 5.5.4.

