## 11.4. Appendix 4: Study Phases and Treatment Emergent Adverse Events

### 11.4.1. Study Phases

Assessments and events will be classified according to the time of occurrence relative to start and/or stop date of the study treatment.

Study Phase	Definition
Pre-Treatment	Date $\leq$ (First) Study Treatment Start Date
On-Treatment	(First) Study Treatment Start Date < Date $\leq$ (Last) Study Treatment Stop Date + 5 days
Post-Treatment	Date > (Last) Study Treatment Stop Date + 5 days

Study epoch of follow-up data for Part 1 will be summarized in following way:

Follow-up from Period 1 will be counted in Period 1 summary;

Follow-up from Period 2 will be counted in Period 2 summary;

Follow-up from Period 3 will be counted in Period 3 summary;

Follow-up from final follow-up will be counted in Period 4 summary.

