### 11.4.2. Treatment Emergent Flag for Adverse Events

Flag	Definition
Treatment Emergent	
 
• If AE onset date is on or after treatment start date & on or before treatment stop date.
 
• Study Treatment Start Date <math>\leq</math> AE Start Date <math>\leq</math> Study Treatment Stop Date
 
• For Part 1: AE onset is during one period and worsens during a later period it would be counted in both periods. For the initial period, the logic would be as above. For the later period the logic would use the treatment dates associated with the later period
 
• Treatment Period Start Date <math>\leq</math> AE Worsening Date <math>\leq</math> Study Treatment Stop Date
 

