**NOTES:**

- If the study treatment stop date is missing, then the AE will be considered to be On-Treatment.
- Time of study treatment dosing and start/stop time of AEs should be considered, if collected.

### 11.4.3. Adverse Events Assignment to Treatment Period for Part 1

Adverse events (AEs) will be assigned to a treatment period and corresponding treatment received in that treatment period after the imputations defined in RAP section 12.7.2 have been performed.

- Treatment Period 1: all AEs with start date/time at the time of or after administration in Treatment Period 1 and before administration in Treatment Period 2
- Treatment Period 2: all AEs with start date/time at the time of or after administration in Treatment Period 2 and before administration in Treatment Period 3
- Treatment Period 3: all AEs with start date/time at the time of or after administration in Treatment Period 3 and before administration in Treatment Period 4
- Treatment Period 4: all AEs with start date/time at the time of or after administration in Treatment Period 4

Thus, AEs occurring during the 1st washout will be assigned to the treatment received in Treatment Period 1, AEs occurring during the 2th washout will be assigned to the treatment received in Treatment Period 2, AEs occurring during the 3rd washout will be assigned to the treatment received in Treatment Period 3 and AEs occurring during final follow-up will be assigned to the treatment received in Treatment Period 4.

### 11.4.4. Concomitant Medication Assignment to Treatment Period for Part 1

Concomitant medications (CMs) will be assigned to a treatment period and corresponding treatment received in that treatment period after the imputations defined in RAP section 12.7.2 have been performed.

- Treatment Period 1: all CMs with start date/time at the time of or after administration in Treatment Period 1 and before administration in Treatment Period 2
- Treatment Period 2: all CMs with start date/time at the time of or after administration in Treatment Period 2 and before administration in Treatment Period 3
- Treatment Period 3: all CMs with start date/time at the time of or after administration in Treatment Period 3 and before administration in Treatment Period 4
- Treatment Period 4: all CMs with start date/time at the time of or after administration in Treatment Period 4

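### Part 1 adverse events with a missing start day are set to the first of the month before the period is assigned, so most of those soon after a Period 2–4 dose are credited to an earlier period's treatment

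*SAP*

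**What the plan says.** SAP 11.7.2.1 covers AE dates recorded as month and year only ("that is, the day of the month may be missing"). For a missing start day, "First of the month will be used unless this is before the start date of study treatment"; otherwise "in this case the study treatment start date will be used". The section introduces these conventions for calculating time to onset and duration.

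SAP 11.4.3 then extends their use. In Part 1 it assigns each AE to a treatment period, and to the treatment given in that period, "after the imputations defined in RAP section 12.7.2 have been performed". Section 12.7.2 does not exist in this SAP; the matching section is 11.7.2. An AE belongs to a period if it starts at or after that period's dose and before the next one.

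Protocol 5.1 says that "a participant in either cohort will receive the next dose after approximately 3 or 4 weeks". SAP 2.3 gives the doses by period as 1, 10, 100 and 400 mg in Cohort 1 and 3, 30, 200 and 700 mg in Cohort 2, with each participant receiving placebo in one of the four periods.

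For a missing stop day, SAP 11.7.2.1 says "Last day of the month will be used, unless this is after the stop date of study treatment", in which case the treatment stop date is used.

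**The concern.** The start-day rule suits a single course of treatment. In a crossover, a floor at the start of study treatment protects Period 1 only. Suppose a participant is dosed in Period 3 on the 15th, has an AE on the 17th, and the day is not recorded. The AE is set to the 1st, which lies in the Period 2 interval, and is counted under the Period 2 treatment. If instead the Period 3 dose is on the 25th and the Period 2 dose was 21 days before, on the 4th, the 1st precedes both doses and the AE is counted under Period 1.

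AEs are part of the primary endpoint, and the Part 1 overview table takes percentages over the participants on each treatment. There are 6 active participants per dose, so one moved event can change a dose column by 1/6 = 16.7 percentage points. Placebo is pooled within each part, so with 16 Part 1 participants the same event is about 1/16 = 6.3 points there.

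**Working it through.** The documents give no figure on this point, so there is none to reproduce.

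**Inputs.** The start-day rule and its floor (SAP 11.7.2.1); imputation before assignment, and the period rule (SAP 11.4.3); gaps of 21 or 28 days (Protocol 5.1); dose order and sequences (SAP 2.3). *Assumptions, not in the documents:* the dosing day is uniform over the calendar, the gap is constant within a participant, and onset is equally likely on each day of the window.

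**Moved to any earlier period.** Take an AE d days after a Period 2–4 dose, in a month of M days. It moves back if the dose falls on the 2nd or later and the AE falls in the same month, so

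P(d) = (M − 1 − d)/M, with mean M = 30.44.

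This is linear in d, so a window's share is P at its mean d:

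| Window after dose | Mean d | Share moved |
|---|---|---|
| Days 0–4 (in unit) | 2 | 27.44/30.44 = 90% |
| Day 5 to next dose, 21-day gap | 12.5 | 16.94/30.44 = 56% |
| Day 5 to next dose, 28-day gap | 16 | 13.44/30.44 = 44% |

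Enumerating every Period 1 dosing date over four years gives 90.1%, 55.6% and 44.1%. No move is forward.

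**Moved two or more periods back.** The previous dose must also fall on the 2nd or later of the same month, and the AE must belong to Period 3 or 4 (2 of the 3 periods at risk). With 21-day gaps and days 0–4, the share is (30.44 − 22 − 2)/30.44 × 2/3 = 0.212 × 2/3 = 14%. The other 76% move one period back. With 28-day gaps, enumeration gives 89% one back and 1% two or more.

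**Direction.** There are 4 sequences × 2 cohorts × Periods 2–4 = 24 cells. For a move of one period:

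| AE arose on | Credited to | Cells |
|---|---|---|
| Active | Lower active dose | 12 |
| Active | Placebo | 6 |
| Placebo | Active dose | 6 |

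All 18 active-origin cells go to a lower dose or placebo. All 6 placebo-origin cells go to an active dose. Moves of two or more periods follow the same pattern, because doses ascend and each participant has only one placebo period.

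**Stop day.** Protocol 9.2.1 collects AEs up to the follow-up visit. An AE that starts after the last dose and lacks a stop day is capped at the treatment stop date, so it ends before it began. Period assignment uses the start date only, so this affects AE duration and not the dose columns.

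**The case against.** **The rule may not be meant for period assignment.** SAP 11.7.2.1 mentions only time to onset and duration. SAP 11.4.3, however, expressly assigns periods after the imputation, and a stale section number does not undo that.

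**The floor might mean the start of the current period.** That would remove the problem, but the text does not support it. SAP 11.4.1 treats the study treatment start as the first one. SAP 11.4.2 has a separate term, "Treatment Period Start Date", which the imputation rule does not use. The period is also unknown until assignment has been done.

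**Few records will be affected, and they will be visible.** This stands. Participants are in the unit from Day −2 to Day 5 under continuous AE review, so a missing day is least likely in the window with the 90% share. In the washout, where it is more plausible, the share is 44–56%. Partial dates are listed as captured, every Part 1 AE is listed, and there are only 16 participants, so a reader could trace an affected record. The 16.7-point shift also requires that the participant has no other AE in that row.

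**Stronger readings.** A reader might infer that the error always flatters the drug. It does not: AEs from a placebo period, 6 of 24 cells, move to an active dose. A reader might also infer that 90% go to the immediately preceding treatment. With 21-day gaps, 76% do.

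**Conclusion.** The gap is real. Following SAP 11.7.2.1 and 11.4.3 as written gives the wrong treatment for most day-missing AEs soon after a Period 2–4 dose: about 90% on days 0–4, and 44–56% in the washout. With 21-day gaps, about 14% of the days 0–4 AEs go two or more periods back. The move is always to an earlier period. It goes to a lower dose or placebo for AEs on active drug, and to an active dose for AEs on placebo.

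The shares are conditional on a missing start day and rest on the uniform-calendar assumption. For Period 4 the washout share is only indicative, because AE collection ends at a follow-up visit 7–14 days after the last dose. The documents show no affected record and few are expected, so they do not support a claim that the Part 1 AE tables are materially biased. This is a minor drafting fault that is cheap to correct. The stop-day fault is separate and smaller.

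**What to change.** In SAP 11.7.2.1, add a rule for Part 1 AEs with a missing start day:

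1. Establish the period first, by site query before database freeze or from a period recorded with the AE if the eCRF holds one (the documents do not say). Impute the first of the month, but no earlier than that period's dosing date. This leaves no misassignment if the period is right.
2. Only if the period cannot be established, use the latest dosing date in the recorded month that is not after a known AE stop date. If there is none, use the first of the month, with the existing floor at the study treatment start date.
3. Flag AEs handled under step 2 in the listing.

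Separately, set a missing stop day to the end of the month, capped at last contact and never before the AE start; this corrects duration only. Change the reference in 11.4.3 from 12.7.2 to 11.7.2.

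**Cost.** One SAP rule, a small programming change and perhaps a few queries. The fallback has a real downside. It removes backward moves, but it can push a true washout AE forward to the next period. Enumerated for AEs from day 5 to the next dose after Periods 1–3, this happens in about 4% (28-day gaps) to 6% (21-day gaps) when the AE lasts one day (stop date the day after onset). It rises to 61–72% when the AE is ongoing or its stop date is unknown. Period 1 AEs, which the present rule places correctly, are among those exposed. Forward is not always the cautious direction either: in 3 of the 9 active-origin transitions per cohort the next period is placebo. For these reasons the query or recorded period comes first.

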9.2.1. Time Period and Frequency for Collecting AE and SAE Information

- All SAEs will be collected from the signing of the ICF until the follow-up visit at the time points specified in the [SoA](#) (Section 2).
- All AEs will be collected from the start of treatment until the follow-up visit at the time points specified in the [SoA](#) (Section 2).
- Medical occurrences that begin before the start of study treatment but after obtaining informed consent will be recorded on the Medical History/Current Medical Conditions section of the case report form (CRF) not the AE section.
- All SAEs will be recorded and reported to the sponsor or designee within 24 hours, as indicated in [Appendix 4](#). The investigator will submit any updated SAE data to the sponsor within 24 hours of it being available.
- Investigators are not obligated to actively seek AEs or SAEs in former study participants. However, if the investigator learns of any SAE, including a death, at any time after a participant has been discharged from the study, and he/she considers the event to be reasonably related to the study treatment or study participation, the investigator must promptly notify the sponsor.
- The method of recording, evaluating, and assessing causality of AEs and SAEs and the procedures for completing and transmitting SAE reports are provided in [Appendix 4](#).

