9.2.3. Follow-up of AEs and SAEs

After the initial AE/SAE report, the investigator is required to proactively follow each participant at subsequent visits/contacts. All SAEs and AEs will be followed until the event is resolved, stabilized, otherwise explained, or the participant is lost to follow-up (as defined in Section 8.3). Further information on follow-up procedures is given in [Appendix 4](#).

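### The SAP limits an imputed AE stop date to the treatment stop date, with no floor at onset, so events with a missing stop day that end after the last dose get truncated, zero or negative durations (minor)

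*SAP*

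**What the plan says.** SAP 11.7.2.1 covers AE dates for which only month and year were recorded. Its stated use is explicit: "the following conventions will be applied for calculating the time to onset and the duration of the event". For a missing stop day the rule is "Last day of the month will be used, unless this is after the stop date of study treatment", and then "in this case the study treatment stop date will be used". Dates that are missing altogether are outside the rule: "Completely missing start or end dates will remain missing, with no imputation applied".

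Protocol 9.2.1 sets the collection window: "All AEs will be collected from the start of treatment until the follow-up visit at the time points specified". Protocol 5.1 puts that visit 7-14 days after the last dose. Protocol 9.2.3 adds: "All SAEs and AEs will be followed until the event is resolved, stabilized, otherwise explained".

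The SAP does not define the treatment stop date by period in 11.7.2.1. Section 11.4.1 defines the on-treatment phase by the last study treatment stop date plus 5 days. Section 11.4.2, for a Part 1 event that worsens in a later period, uses the treatment dates of that later period. Section 11.4.3 assigns AEs to periods after imputation, and gives events in the final follow-up to the Period 4 treatment.

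**The concern.** The imputed stop date is the earlier of two dates, and one of them, the treatment stop, precedes part of the period in which AEs are collected. An event that runs past the last dose is then recorded as ending with that dose. An event that begins after the last dose is recorded as ending before it began. This also sits badly with the SAP's own conventions, which treat the 5 days after the last dose as on-treatment and attribute final follow-up events to the Period 4 treatment.

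What is at stake is the derived AE duration. In Part 1 there is a further question: whether durations are handled the same way across dose levels. That depends on which treatment stop date is meant, and the SAP leaves it open.

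**Working it through.** There is no plan figure to reproduce; the check applies the rule as written.

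**Inputs**
- Imputed stop = min(last day of the recorded stop month, treatment stop date): SAP 11.7.2.1.
- Part 2: 14 daily doses, so treatment stops on Day 14; follow-up is on Day 21-28: Protocol 5.1.
- Part 1: one dose per period on that period's Day 1, with doses about 3 or 4 weeks apart; follow-up after Period 4 falls on Day 8-15: Protocol 5.1. Period 4 is 400 mg in Cohort 1 and 700 mg in Cohort 2 (SAP 2.3), with 6 active and 2 placebo participants in each.
- Duration = stop - start + 1. This is an assumption: the SAP gives no AE duration formula, but 11.6.2 counts exposure days this way.

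**When the limit binds.** If an event truly ends after the last dose, the end of its stop month is also after the last dose. The treatment stop date therefore always replaces month end for such an event when its stop day is missing.

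**Part 2.** With onset on Day d, the imputed duration is 14 - d + 1 = 15 - d.
- Onset Day 12, true end Day 20: imputed 15 - 12 = 3 days against a true 20 - 12 + 1 = 9.
- Onset Day 14: 1 day. Day 15: 0. Day 16: -1.

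**Part 1, Period 4.** The limit is the dosing day, so the imputed duration is 1 - d + 1 = 2 - d, whatever the true duration.
- Onset Day 1: 1 day. Day 2: 0. Day 3: -1. Day 5: -3.

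**Part 1, Periods 1-3.** There are two readings.
- Study-level stop date: the limit is the Period 4 dosing day, weeks later, so month end normally stands and the event is not shortened.
- Period-level stop date: the limit is that period's own dosing day, and 2 - d applies in every period.

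**Illustration.** The rule was run over every calendar start day of one year, with dose gaps of 21, 24 and 28 days, true durations of 2-7 days, and onsets 0-4 days after a Part 1 dose or on Days 1-18 in Part 2. Onsets and durations are assumed and equally weighted, and every stop day is taken as missing.

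| Group | Shortened | Duration 0 or less | Negative | Mean error (days) |
|---|---|---|---|---|
| Periods 1-3, study-level | 0% | 0% | 0% | +11.2 to +14.7 |
| Period 4, study-level | 100% | 80% | 60% | -5.5 |
| Periods 1-4, period-level | 100% | 80% | 60% | -5.5 |
| Part 2 | 42% | 22% | 17% | +0.6 |

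The Period 4 row can be checked by hand: onsets on Days 1-5 give 1, 0, -1, -2 and -3, mean -1, against a mean true duration of 4.5, so the error is -5.5. The positive errors come from the month-end rule itself, which overstates duration when nothing limits it.

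**The case against.** The strongest reply is that no planned result visibly uses the value. The AE summaries in SAP 7.2.1 and the AE tables in 11.12.5 (3.1-3.8 and 3.28-3.35) cover incidence, grade, relatedness, seriousness, special interest and withdrawal; none is titled as a summary of duration. Listings show partial dates as captured. The treatment-emergent flag (11.4.2) and period assignment (11.4.3) use the start or worsening date. All of this stands. What remains open is whether the listing shells, which are not in the documents, print a derived duration.

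Three stronger readings are tempting, and the documents do not support them.

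- A reader might infer that events at the two highest single doses are made to look shorter than those at lower doses. That needs a study-level stop date. Section 11.4.1 and the order of steps in 11.4.3 favour it, but 11.7.2.1 does not define the term and 11.4.2 uses period dates in a related case. On a period-level reading the contrast disappears and the truncation spreads to every period. Period 4 also includes placebo.
- A reader might infer that every AE starting after the last dose gets a negative duration. Only events with a missing stop day are affected, and an onset on the day after the last dose gives 0. If the start day is missing too, onset may be imputed to the first of the month, which can lengthen the event instead.
- A reader might take the share of Part 2 collection days after the last dose, 7/21 to 14/28 (33-50%), as the share of events affected. It counts calendar days. Participants stay in the unit to Day 18, so the days after discharge are 3/21 to 10/28 (14-36%), and the documents do not say how often a stop day will be missing.

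**Conclusion.** The rule is wrong as written, not just underspecified: it is meant to yield durations, and for events with a missing stop day that end after the last dose it returns a shortened, zero or negative value. This follows from the SAP and protocol text alone; the exact zeros and negatives also assume the stop - start + 1 convention.

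The dose pattern in Part 1 is conditional: confined in practice to Period 4 if the stop date is study-level, equal across periods if it is period-level.

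The point is minor. It reaches only derived durations of AEs with a missing stop day, whose number is unknown and may be small in a largely inpatient study. The analysis of the primary safety endpoint by incidence and grade is untouched.

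**What to change.** Replace the missing-stop-day rule in SAP 11.7.2.1. Impute the stop date as the earlier of the last day of the recorded month and the last study contact for that period, and never before the (imputed) AE start date. Define last contact as follows.

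- Part 1, Periods 1-3: the last contact before the next period's dose, or the next dosing date if the event is known to continue to it.
- Part 1, Period 4, and Part 2: the follow-up visit or last contact.

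The limit has to be set by period. Using only the final follow-up visit would leave Periods 1-3 running to month end while Period 4 was held to 7-14 days after dosing.

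Under this rule a Part 2 event starting on Day 16, with follow-up on Day 28 and month end later, would be given 28 - 16 + 1 = 13 days in place of -1.

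The cost is one line of SAP text and the matching program line, with no effect on study conduct. There is a small downside: month-end imputation can still overstate duration, though now within the collection window. That window remains longer in Periods 1-3 (up to the next dose, about 3 or 4 weeks) than after Period 4.
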